3.5.2 Phase I and II – Cycle 2 – beyond

Procedure	Cycles 2-3					Cycles $\geq 4$			At Disease Progression	End of Treatment	Post-therapy follow-up 	End of Study
	Day 1	Day 8	Day 15	Day 22	Day 28	Day 1	Day 8	Day 28				
Window(s):	-3 days	$\pm 3$ days	$\pm 3$ days	$\pm 3$ days	$\pm 3$ days	-3 days	$\pm 3$ days	$\pm 3$ days	$\pm 3$ days	$30+7$ days	See note.	
Physical exam	X		X			X				X		
Vital signs 	X		X			X				X		
Height												
Weight	X		X			X				X		
Performance score												
Chemistries 	X		X			X			X	X		
CBC/differential	X		X			X			X	X		
Reticulocyte count	X					X			X	X		
Pregnancy test	X					X						
Urinalysis	X					X				X		
Bone marrow biopsy and aspirate 					X 			X 	X			
TBNK panel 	X					X			X	X		
Peripheral blood flow cytometry									X 			
Next gen seq- myeloid panel					X 			X 	X			
Correlative research studies (see Section 5.1)	X		X 		X 	X		X 	X	X		
Inqovi administration 	X					X						
KPT-8602 administration 		X	X				X					
Response evaluation 	X					X						
Transfusion dependency assessment	X		X			X			X	X		
Adverse event assessment	X	X	X	X	X	X		X	X	X		
Concomitant-medications	X		X			X				X		
PRO: NIH MDS Adult Psychosocial assessment 					X			X		X		
PRO: EORTC-QLQC30 	X				X	X		X	X	X	X	
PRO: PRO-CTCAE 	X	X	X	X	X	X		X	X	X	X	
PRO: Overall Side Effect Bother 					X	X		X	X	X	X	
PRO: PROMIS Physical Function 	X	X	X	X	X	X		X	X	X	X	
PRO: PGI-S 	X	X	X	X	X	X		X	X	X	X	

Procedure	Cycles 2-3					Cycles ≥4			At Disease Progression	End of Treatment	Post-therapy follow-up 	End of Study
	Day 1	Day 8	Day 15	Day 22	Day 28	Day 1	Day 8	Day 28				
Window(s):	-3 days	±3 days	±3 days	±3 days	±3 days	-3 days	±3 days	±3 days	±3 days	30+7 days	See note.	
PRO: PGI-C 					X	X		X	X	X	X	
Survival											X	X

Follow-up will occur via phone call every 3 months (+/- 2 weeks) for the first 24 months, then every 6 months (+/- 4 weeks) for 3 years, then annually for up to 8 years. Overall survival, event-free survival, progression-free survival, and treatment status will be assessed at all timepoints.

Includes temperature, blood pressure, heart rate, respiratory rate, oxygen saturation

Includes sodium, chloride, potassium, CO2, BUN, creatinine, glucose, AST/ALT, alkaline phosphatase, total bilirubin, direct bilirubin, albumin, total protein, magnesium, phosphorous, calcium, LDH, uric acid for all timepoints beyond screening and baseline

Bone marrow core biopsy will be sent for pathologic evaluation. Bone marrow aspirate will be sent for flow cytometry and additional studies per Section 5.1.

Required for Phase II, C2D28 +/- 3 days. Additional timepoints as clinically indicated

Required for Phase II, C6D28 +/- 3 days. Additional timepoints as clinically indicated

CD3, CD4, CD8, C19 clinical panel.

If evidence of peripheral blood blasts

Required for Phase II, C2D28 +/- 3 days. Additional timepoints as clinically indicated

Required for Phase II, C6D28 +/- 3 days. Additional timepoints as clinically indicated

Sparse PK sampling for all participants on C2D15 and C3D15 to be drawn prior to taking dose (trough).

On day of bone marrow biopsy, if being performed.

On day of bone marrow biopsy, if being performed.

HR-MDS cohorts (Cohorts 1 & 2): administer Inqovi orally once daily on Days 1-5 of each 28-day cycle.

Administer KPT-8602 according to dose level assigned to each participant (see Section 3.3)

Assessment of response to therapy, based on peripheral blood counts +/- bone marrow results (if done).

NIH MDS Adult Psychosocial Assessment to be completed at C12D28 (+/- 1 day), C24D28 (+/- 1 day) and end of treatment.

EORTC-QLQC30 to be completed by participants at C3D28 (+/- 1 day), C6D28 (+/- 1 day), C9D28 (+/- 1 day), C12D28 (+/- 1 day), C24D28 (+/- 1 day) and end of treatment. See Section 3.4.3

PRO\_CTCAE, PROMIS PF 10b, and PGI-S will be completed at baseline, weekly for cycles 1 through 3 on D8 (+/- 7 days), D15 (+/- 7 days), D22 (+/- 7 days) and D28 (+/- 7 days), C6D28 (+/- 7 days), C9D28 (+/- 7 days), C12D28 (+/- 7 days), C24D28 (+/- 7 days), at disease progression, and end of treatment. See Section 3.4.3.

FACIT Bother and PGI-C done weekly for cycles 1 through 3 on D28 (+/- 7 days), D15 (+/- 7 days), D22 (+/- 7 days), D28 (+/- 7 days), C6D28 (+/- 7 days), C9D28 (+/- 7 days), C12D28 (+/- 7 days), C24D28 (+/- 7 days), at disease progression, and end of treatment. See Section 3.4.3.

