Eltanexor (KPT-8602) is a second-generation, slowly reversible, orally bioavailable SINE compound, currently in Phase 1/2 development. It has similar potency to selinexor *in vitro* against XPO1-mediated transport and in cancer cell lines. However, it has a distinct pharmacology related to its unique chemical structure resulting in substantially lower brain penetration when compared with selinexor: ~30-fold lower in monkey studies. In animal models, this resulted in lower levels of anorexia and weight loss and permitted eltanexor once daily dosing for 5 consecutive days each week. It also exhibited superior anti-leukemic activity in *in vitro* studies of AML cell lines, and was associated with improved survival in a human xenograft model of AML. Preclinical studies also showed that eltanexor is minimally toxic to normal hematopoietic stem and progenitor cells, and eltanexor did not accumulate in plasma after repetitive dosing. The improved tolerability of eltanexor may be due to its reduced brain penetration and improved therapeutic window. The safety, tolerability, and preliminary efficacy of eltanexor is currently under investigation in Study KCP-8602-801 (hereafter referred to as Study 801, NCT02649790) which is an ongoing first-in-human, open-label dose-escalation study in patients with relapsed/refractory multiple myeloma

(R/R MM) followed by a dose-expansion phase in patients with select advanced malignancies, including mCRC, mCRPC, and HR-MDS.

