#### 1.2.3.3 Pharmacokinetic (PK) and pharmacodynamic (PD) data

In Study 801, the PK profile of KPT-8602 (eltanexor) after oral administration was predictable, dose-proportional, and exhibited moderate inter-patient variability across doses of 5-20 mg in male and female patients with R/R MM, mCRC, mCRPC, and HR-MDS. Following single doses of 5-60 mg at C1D1, the eltanexor PK profile was characterized by rapid absorption (median  $T_{max}$  1-3 hours) and moderate clearance (21-35 L/h), volume of distribution 170-264 L, and terminal half-life 4-6 hours. Interindividual variability was moderate as evidenced by geometric mean percent coefficient of variation (%CV) values (range) for  $AUC_{0-\infty}$  24-44% and  $C_{max}$  15-53% (Eltanexor IB, version 4.0).

[figure not shown]
Based on nonclinical and exploratory clinical data from SINE compounds, the change in XPO1 mRNA expression after treatment is an appropriate PD marker and was used to evaluate target engagement across the first 6 R/R MM cohorts treated with single-agent eltanexor on Study 801. Target engagement was assessed from whole blood collected on C1D1 at 2, 4, 8, and 24 hours post dose of eltanexor and was compared to the relative level (i.e., set to 1 at 0 hrs) at pre-dose. The plasma concentration of eltanexor was also calculated and plotted. For all cohorts evaluated, the fold-change maximum ( $F_{max}$ ) of XPO1 mRNA expression was achieved 4 to 8 hours post-dose. The  $F_{max}$  and  $AUC_{24}$  for XPO1 mRNA was roughly dose proportional to the  $C_{max}$  and  $AUC_{24}$  of eltanexor in plasma samples from these patients. The plateau for  $F_{max}$  and  $AUC_{24}$  of XPO1 mRNA in treated patients was 5-fold change and 100-fold change (baseline\*hr), respectively, when compared with pre-dose levels. Based on these preliminary data, the maximum dose for these XPO1 changes occurs in patients treated with 60 mg of eltanexor. Although the RP2D of 20-30 mg eltanexor (depending on the indication) does not maximize the  $F_{max}$  at C1D1, this reduced response of XPO1 mRNA may correlate with the improved tolerability of eltanexor. Of note, there is currently not enough data for a clinically reliable marker of maximal pharmacologic activity for eltanexor. We will use the MTD to make our RP2D determination and use the totality of data from

this early phase trial, including PK, PD, safety and MTD interpretation to best determine optimal dosing in later trials.

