### 3.1.2 Dose Escalation

In a phase I/II study (NCT 02649790) that evaluated single agent eltanexor in higher-risk MDS, 2 doses were evaluated: 5 patients received 10 mg and 15 patients received 20 mg, every day for 5 days per week of a 28-day cycle. The majority of patients were aged  $\geq 75$  and all were treated and refractory to hypomethylating agents. None of the patients experienced dose-limiting toxicities (DLTs) and the RP2D for eltanexor was selected as 10 mg given on days 1-5 of each week of a 28-day cycle in HR-MDS (20/28 days). Given the overlap in toxicities, particularly hematologic, between hypomethylating agents and eltanexor, our starting dose was set at 10 mg PO daily on Days 8-12 and Days 15-19 (total of 10 days per 28-day cycle as opposed to 20 days per 28-day cycle in NCT 02649790).

In Phase I, dose escalation will proceed in cohorts of 3-6 participants. The MTD is the dose level at which no more than 1 of up to 6 participants experience DLT during the first cycle (28 days) of treatment, and the dose below that at which at least 2 (of  $\leq 6$ ) participants have DLT as a result of the drug.

Participants in Cohort 1 will be eligible for the DLT evaluation if  $\geq 90\%$  (9 out of 10 doses) of KPT-8602 and  $\geq 80\%$  (4 out of 5 doses) of Inqovi were taken within the DLT period. Participants not evaluable for toxicity, will be replaced in the dose level.

Dose Escalation Schedule	
Dose Level	Dose of KPT-8602
Level -2	5 mg PO daily on Days 8-12 and Days 15-19
Level -1	5 mg PO daily on Days 8-21
Level 1 (starting dose)	10 mg PO daily on Days 8-12 and Days 15-19
Level 2	10 mg PO daily on Days 8-21

Dose escalation will start at dose level 1 and follow the rules outlined in the Table below.

Number of Participants with DLT at a Given Dose Level	Escalation Decision Rule
0 out of 3	Enter up to 3 participants at the next dose level
$\geq 2$	Dose escalation will be stopped. This dose level will be declared the maximally administered dose (highest dose administered). Up to three (3) additional participants will be entered at the next lowest dose level if only 3 participants were treated previously at that dose.

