### 5.1 BIOSPECIMEN COLLECTION

Test/assay	Volume (approx.)	Type of sample/tube(s) ^	Collection point	Location of specimen analysis
Pharmacokinetics (PK)	4 mL	Blood, SST vacutainer tubes -Serum samples should then be	Dose levels -2 and 1: C1D8 (1)Pre-dose, (2) 1 hr ( $\pm$ 10 min) post-dose, (3) 2 hr ( $\pm$ 10 min) post-dose, (4) 3 hr ( $\pm$ 10 min) post-dose,	Clinical Pharmacology Program (CPP) ; [name] laboratory

Test/assay	Volume (approx.)	Type of sample/ tube(s) ^	Collection point	Location of specimen analysis
		transferred to micronic tubes for shipping to bioanalytical lab.	
(5) 4 hr (<math>\pm</math> 20 min) post-dose, (6) 8 hr (<math>\pm</math> 20 min) post-dose, (7) 24 hr (<math>\pm</math> 1 hr) post-dose (8) 24 hr (<math>\pm</math> 1 hr) post-dose-i.e, C1D9 pre-dose
 
C1D12 (9) Pre-dose, (10) 2 hr (<math>\pm</math> 10 min) post-dose, (11) 3 hr (<math>\pm</math> 10 min) post-dose, (12) 8 hr (<math>\pm</math> 20 min) post-dose, (13) 24 hr (<math>\pm</math> 1 hr) post-dose-i.e, C1D13 pre-dose, (14) 48 hrs (<math>\pm</math> 2hr) post-dose- i.e, C1D14 pre-dose
 
Dose levels -1 and 2:
 
C1D8 (1)Pre-dose, (2) 1 hr (<math>\pm</math> 10 min) post-dose, (3) 2 hr (<math>\pm</math> 10 min) post-dose, (4) 3 hr (<math>\pm</math> 10 min) post-dose, (5) 4 hr (<math>\pm</math> 20 min) post-dose, (6) 8 hr (<math>\pm</math> 20 min) post-dose, (7) 24 hr (<math>\pm</math> 1 hr) post-dose i.e, C1D9 pre-dose
 
C1D21 (9) Pre-dose, (10) 1 hr (<math>\pm</math> 10 min) post-dose, (11) 3 hr (<math>\pm</math> 10 min) post-dose, (12) 4 hr (<math>\pm</math> 20 min) post-dose, (13) 8 hr (<math>\pm</math> 20 min) post-dose, (14) 24 hr (<math>\pm</math> 1 hr) post-dose-i.e, C1D22 pre-dose, (15) 48 hrs (<math>\pm</math> 2hr) post-dose- i.e, C1D23 pre-dose
 
Sparse PK sampling for all participants:
 
C2D15, C3D15 trough dosing to be drawn prior to taking dose that day.
	
Pharmacodynamics (PD):	2.5 mL	Blood, Paxgene RNA tube	Phase I: C1D8 (1)Pre-dose, (2) 1 hr ( $\pm$ 10 min) post-dose, (3) 2 hr ( $\pm$ 10	Clinical Pharmacology

Test/assay	Volume (approx.)	Type of sample/tube(s) ^	Collection point	Location of specimen analysis

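### At dose levels 1 and -2 the C2D15/C3D15 trough PK sample nominally falls 72 h after the last dose, so it carries almost no exposure information and is not comparable with the 24 h trough at levels 2 and -1

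*Combined protocol and SAP*

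**What the plan says.** Two places set the sparse sampling rule, and neither separates the dose levels:

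- Section 3.5.2, footnote 11: "Sparse PK sampling for all participants on C2D15 and C3D15 to be drawn prior to taking dose (trough".
- Section 5.1, PK row: "C2D15, C3D15 trough dosing to be drawn prior to taking dose that day".

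Section 3.1.2 defines two dosing patterns, and Section 3.3.1 repeats them for toxicity management:

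- Level 1, the starting level: "10 mg PO daily on Days 8-12 and Days 15-19". Level -2: "5 mg PO daily on Days 8-12 and Days 15-19". Neither has a dose on Days 13 and 14.
- Level 2: "10 mg PO daily on Days 8-21". Level -1 uses the same days at 5 mg.

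Section 1.2.3.3 summarises single-dose PK as "moderate clearance (21-35 L/h), volume of distribution 170-264 L, and terminal half-life 4-6 hours". Section 1.2.3.1 adds, from preclinical work, that "eltanexor did not accumulate in plasma after repetitive dosing".

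Section 5.2.1.2 applies the Phase I PK schedule to Phase II at the RP2D. Section 5.2.1 requires actual dose and sample times to be recorded. Under Section 5, PK samples are the only research samples that are not optional.

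**The concern.** A trough is the concentration at the end of a dosing interval. At levels 2 and -1 the Day 15 pre-dose draw is exactly that, 24 h after the Day 14 dose. At levels 1 and -2 it comes at the end of a two-day break, when a drug with a half-life of a few hours has almost gone.

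The cycle 1 schedule was fitted to the dosing pattern: the second profile is on Day 12 for levels 1 and -2, and on Day 21 for levels 2 and -1 (Section 3.5.1, footnotes 15 and 16; Section 5.1). The sparse rule did not get that split. Section 5.1 also labels the 24 h and 48 h samples after Day 12 at levels -2 and 1 as pre-dose on C1D13 and C1D14, although those levels have no dose on those days. This suggests that the break was overlooked.

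At stake is the only scheduled check on exposure after cycle 1, and any use of it in the exploratory exposure-response work (Section 1.1.3). Level 1 is the starting level, so the problem applies from the first participant.

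**Working it through.** **1. Inputs.** Dosing days from Section 3.1.2; half-life 4-6 h, clearance (CL) 21-35 L/h and volume (V) 170-264 L from Section 1.2.3.3; sampling day from Sections 3.5.2 and 5.1. The documents state no dose-to-sample interval for the sparse draw.

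**2. Check of the stated half-life.** t½ = ln 2 × V / CL.

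- Low V with low CL: 0.693 × 170 / 21 = 5.6 h.
- High V with high CL: 0.693 × 264 / 35 = 5.2 h.

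Both lie within 4-6 h. The extreme cross-pairings give 3.4 h (170 with 35) and 8.7 h (264 with 21).

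**3. Nominal interval.** 24 h × (15 − last dosing day before Day 15).

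- Levels 1 and -2: 24 × (15 − 12) = 72 h.
- Levels 2 and -1: 24 × (15 − 14) = 24 h.

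**4. Fraction remaining.** 0.5^(interval / t½).

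| Levels | Interval | t½ = 4 h | t½ = 6 h |
|---|---|---|---|
| 1, -2 | 72 h | 0.5^18 = 0.0004% | 0.5^12 = 0.024% |
| 2, -1 | 24 h | 0.5^6 = 1.6% | 0.5^4 = 6.3% |

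The 24 h to 72 h ratio is 2^(48/t½): 2^12 = 4,096 at 4 h and 2^8 = 256 at 6 h.

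**5. Earlier doses in the cycle.** Summing first-order decay over all doses since Day 8, as a percentage of the single-dose starting concentration C0 = dose / V, gives 0.0004%-0.026% at levels 1 and -2 and 1.6%-6.7% at levels 2 and -1. Carry-over does not change the picture.

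**6. Approximate concentrations.** These assume one compartment and no absorption lag. At 10 mg, C0 is 10,000 µg / 264 L = 37.9 ng/mL to 10,000 µg / 170 L = 58.8 ng/mL. The 72 h value is about 0.00015-0.015 ng/mL and the 24 h value about 0.6-3.9 ng/mL. At 5 mg, halve both.

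**7. Sensitivity.** At the extreme half-life of 8.7 h, 0.38% of C0 remains at 72 h (about 0.14-0.22 ng/mL at 10 mg) and 17.3% at 24 h. That is still a 46-fold gap from timing.

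**8. Visit window.** Sections 3.4.1 and 3.5.2 allow ±3 days for this visit. At levels 1 and -2, a draw before any dose that day comes 24 h after the last dose on Days 12, 13 and 16-18, 48 h after it on Day 14, and 72 h after it on Day 15.

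**The case against.** The strongest reply is that little depends on these samples. The secondary PK endpoints are tied to cycle 1 sampling (Section 10.1), and Section 10.4.3 analyses AUC, half-life and Css by dose level without mentioning the sparse draws. Phase II participants also have the intensive cycle 1 profiles, which exposure-response work can use. No decision rule uses C2D15 or C3D15, and no pooling of sparse values across levels is specified. All of this stands. A reader might infer that the secondary PK objective is compromised; the documents do not support that.

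A reader might also infer that the 72 h samples are known to be unquantifiable. No assay limit is given, so that is an inference from the size of the residual.

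Nor can one say that all later-cycle PK at these levels is lost. The 72 h gap is nominal. A visit moved within the window can give 24 or 48 h, and so can a missed dose made up on Day 13 or 14 under the rule in Section 3.2.1 that extends dosing. Recorded times let the analyst tell these apart. But shifts that happen by chance mix 24, 48 and 72 h values under one label, and recorded times cannot restore information to a 72 h sample.

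Finally, the reach into Phase II is conditional. If level 2 shows no DLTs it becomes the RP2D (Section 3.1.3), and the draw is a 24 h trough for participants who stay there.

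**Conclusion.** The mismatch is real, and it follows from the protocol's own dosing days and half-life. On the nominal schedule, the mandatory C2D15 and C3D15 samples at levels 1 and -2 are taken 12-18 half-lives after the last dose. They differ 256- to 4,096-fold from the true troughs at levels 2 and -1 because of timing alone.

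The damage is limited to the sparse samples in cycles 2 and 3, and to any exposure-response use of them. It affects Phase I participants at levels 1 and -2, and anyone at level 2 who is reduced to level 1 or -2 before these draws. It reaches Phase II as a whole, up to 43 evaluable participants, only if level 1 or -2 becomes the RP2D. A participant reduced from level 1 to level -1 returns to a 24 h interval.

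The result assumes first-order elimination at the stated half-life, with dosing and visits on their nominal days. It does not depend on an assay limit. This is a modest defect, worth correcting because the blood is drawn anyway.

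**What to change.** Split the sparse sampling rule by dose level in both footnote 11 of Section 3.5.2 and the Section 5.1 table, as cycle 1 already does. Levels 2 and -1 can keep the Day 15 pre-dose draw. For levels 1 and -2, choose one of:

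- a pre-dose draw on a day preceded by a dose (Days 16-18 already lie within the Day 15 window); or
- a timed post-dose sample after the in-clinic Day 15 dose, in place of the pre-dose one, for example within the 1-3 h Tmax range in Section 1.2.3.3.

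The choice depends on what the sparse samples are for, which the documents do not say and should. State also that a 72 h value is neither labelled nor pooled as a trough, and that sparse concentrations are analysed by actual time since the last dose, using the times recorded under Section 5.2.1. The pre-dose labels for C1D13 and C1D14 at levels -2 and 1 in Section 5.1 should be reconciled with the dosing days in the same edit.

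The cost is a text change in two sections, plus either a visit 1-3 days later or a wait of 1-3 hours. Replacing the sample needs no extra tube; adding one would need a second tube per visit. No dose, dosing day or clinical rule changes.

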## **3.6 COST AND COMPENSATION**

### **3.6.1 Costs**

NIH does not bill health insurance companies or participants for any research or related clinical care that participants receive at the NIH Clinical Center. If some tests and procedures are performed outside the NIH Clinical Center, participants may have to pay for these costs.

### **3.6.2 Compensation**

Participants will not be compensated on this study.

### **3.6.3 Reimbursement**

The NCI will cover the costs of some expenses associated with protocol participation. Some of these costs may be paid directly by the NIH and some may be reimbursed to the participant/guardian as appropriate. The amount and form of these payments are determined by the NCI Travel and Lodging Reimbursement Policy.

## **3.7 CRITERIA FOR REMOVAL FROM PROTOCOL THERAPY AND OFF STUDY CRITERIA**

Prior to removal from protocol therapy, effort must be made to have all participants complete a safety visit approximately 30 days after the last dose of study therapy (i.e., End of Treatment Visit – see Study Calendar [Section [3.5](#)]).

### **3.7.1 Criteria for removal from protocol therapy**

- Progressive disease
- Participant requests to be withdrawn from active therapy
- Toxicities (see Section [3.3.2](#))
- Lack of, at least partial remission, after 6 cycles of therapy
- Investigator discretion
- Positive pregnancy test

### **3.7.2 Off-Study Criteria**

- Off treatment and completed follow-up on study (i.e., all participants will be followed for 8 years, or until death, whichever comes first)
- Participant requests to be withdrawn from study
- Death
- Screen failure
- Lost to follow-up
- Study is cancelled for any reason

### 3.7.3 Lost to Follow-up

A participant will be considered lost to follow-up if they fail to return for 3 scheduled visits or respond to follow-up phone calls/is unable to be reached by the study site staff.

The following actions must be taken if a participant fails to return to the clinic for a required study visit:

- The site will attempt to contact the participant and reschedule the missed visit within 30 days and counsel the participant on the importance of maintaining the assigned visit schedule and ascertain if the participant wishes to and/or should continue in the study.
- Before a participant is deemed lost to follow-up, the investigator or designee will make every effort to regain contact with the participant (where possible, 3 telephone calls and, if necessary, an IRB-approved certified letter to the participant's last known mailing address or local equivalent methods). These contact attempts should be documented in the participant's medical record or study file.

Should the participant continue to be unreachable, he or she will be considered to have withdrawn from the study with a primary reason of lost to follow-up.

## 4 CONCOMITANT MEDICATIONS/MEASURES

### 4.1 ALLOWED CONCOMITANT MEDICATIONS/SUPPORTIVE MEASURES

#### 4.1.1 Antimicrobial Prophylaxis

- Per standard of care supportive measures for participants with MDS, standard antimicrobial prophylaxis will be considered for neutropenic participants who exhibit ANC <1000 cells/mcL for  $\geq 7$  days prior to study enrollment, either initiation of continuation of prior supportive therapy, including but not limited to:
  - antibacterial prophylaxis with levofloxacin 750 mg daily
  - antiviral prophylaxis with acyclovir 800 mg twice daily
- For participants with clinical indication administration of anti-*Pneumocystis jiroveci* pneumonia prophylactic therapy is allowed.
- For participants with history of fungal infection, or other clinical indication, continuation of antifungal prophylaxis will be allowed.

